3. OBJECTIVES. The objectives of the main study are 1) to conduct a formative assessment to guide adaptations of the current intervention components to optimize implementation of tobacco dependence treatment, 2) to conduct a 3-arm randomized controlled trial (RCT) that compares the effectiveness of three multi-component interventions that are embedded in HIV OPCs, and 3) to assess barriers and facilitators to implementation and potential for sustaining gains. (See schematic above). The objectives of the supplement are 1) to estimate the difference in household food insecurity among PLWH who smoke compared with PLWH who are non-smokers at baseline. 2) to examine mechanisms linking smoking and household food insecurity among PLWH at baseline and 6-months follow-up, and 3) to assess the impact of a reduction in tobacco use and tobacco cessation on measures of food Insecurity at 6-month follow-up.

4. STUDY DESIGN and ENDPOINTS

4.1 DESCRIPTION OF STUDY DESIGN. This is a phase 3 pragmatic comparative effectiveness study. **AIM 1:** We will collect pretrial data using individual interviews with tobacco users to inform further tailoring of the intervention for HIV+ smokers and individual interviews (n=28) with health care providers in three OPCs. We will then conduct a pilot test of ARM 1 and 3 in one OPC with 16 patients. **AIM 2:** We will then conduct a 3-arm RCT to compare the effectiveness of three multi component interventions: 1) Ask, Advise, Assist (AAA) + Refer to the national smokers' Quitline); 2) AAA+Counseling (Counsel) which adds referral to an onsite health worker for 6-sessions of cessation counseling tailored to PLWH; and 3) Addition of 6-weeks of nicotine gum (AAA+Counsel+N). Only ARM 3 participants will receive NRT. ARM 2 and 3 will receive two text messages daily for 8 weeks and then 1 per day for 4 weeks to reinforce the counseling protocol. A total of 747 participants will be recruited in 13 outpatient HIV clinics (OPCs) in Hanoi and randomized into one of the three arms (48 smokers per site, 16 per arm; about 5 non-smokers per site). The primary outcome for smokers is 6-months biochemically validated smoking abstinence. We will conduct baseline in person surveys with all providers (n=98).

AIM 3: We will conduct 12-month post intervention interviews and 18-month surveys with healthcare providers and other key informants to assess factors associated with implementation effectiveness and potential for sustainability.

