6.3. STUDY INTERVENTION ARMS

6.3.1. *Randomization*

Once RAs enroll a patient in the study and the baseline survey is completed (i.e., signed consent), they will use a preprogrammed system in REDCap to randomize patients to one of the three study arms. Our biostatistician will create the REDCap database that will prompt randomization to the appropriate condition.

6.3.2. *Administration of Intervention.* Below we describe the protocol for the RCT intervention components. The materials related to the intervention described below (i.e., brochures, counseling manual and counseling session tracking booklet) will only be used after NYULH and local site IRB approval are obtained for these documents.

ARM 1. Ask, Advise, Assist (AAA) and Refer. The research team will send patient contact information to the Quitline which will proactively call the patient. We will train providers and develop a tool kit that will include information for providers and patients.

ARM 2: AAA plus referral to onsite counselor (Counsel). Multisession counseling: We will

Table 2. Counseling protocol		
Sess.	Wk	Content
1	1	Build motivation, significance of quitting for HIV+ smokers, elicit triggers, quit plan
2	2	Dealing with withdrawal, managing stress, refusal skills
3	3	Managing high risk situations (e.g., other substances), coping with thoughts and feelings
4	4	Review problem solving, stress management and building social support
5	8	Maintaining commitment and motivation, anticipating and preventing slips
6	12	Successes and challenges, long term relapse prevention

provide a packet for each patient randomized to ARM 2 or 3 to the designated nursing staff that has been trained to provide the counseling intervention that includes all intervention handouts. The nurse counselor will receive a manual, session tracking booklet and fidelity checklist. Nurse manuals will include additional information about NRT to be reviewed with patients in ARM 3 and a document to use to track the use of the nicotine

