gum during each session. Our decision to train nurses is consistent with the staffing infrastructure, recommendations from the OPC directors and Provincial health directors and [name] experience working in these sites. Participants will receive six sessions of in person and telephone counseling depending on their preferences (**Table 2**). There is evidence that a greater number of sessions may be associated with higher smoking abstinence rates among PLWH, but these outcomes are short-term (3 month), with a loss of effect by 6 months. Therefore, there is no definitive research on the optimal number of sessions that will lead to long-term outcomes in PLWH. Rather, the literature suggests that it is not only the number of contacts but also the timing (i.e., need for contact over a longer period of time to maintain abstinence).⁴⁻⁸ Therefore, the number of sessions and timing is based on an extensive review timing (i.e., need for contact over a longer period of time to maintain abstinence).⁴⁻⁸ Therefore, the number of sessions and timing is based on an extensive review of the literature, including relevant research conducted by [name] (consultant) among PLWH in Viet Nam⁹⁸ and our pilot research that explored feasibility based on patient and counselor time demands.

Patients will receive 4 sessions in the first 4 weeks and sessions at 8 and 12 weeks that focus on maintaining long-term abstinence (**Table 2**). The first session will last 45 minutes and the following sessions about 30 minutes each. The first session will be scheduled within one week, with sessions 2 through 4 scheduled weekly and the two additional sessions scheduled for weeks 8 and 12. The counseling manual, tailored to PLWH in Viet Nam, will integrate motivational interviewing techniques with a social cognitive skills building approach, both of which have been found effective in increasing long-term abstinence in general populations of smokers and short-term abstinence in PLWH and in smokers enrolled in the VQUIT counseling intervention.⁴⁻¹⁵

ARM 3: AAA+Counsel+N (Nicotine gum). At the end of the first session patients will be taken to the pharmacists who will give participants the first week supply of nicotine gum and a one-page instruction sheet on use, potential side effects and who to call if they have concerns. ARM 2 and 3 will receive two text messages daily for 8 weeks and then 1 per day for 4 weeks to reinforce the counseling protocol.

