8. ASSESSMENT OF SAFETY

8.1 SPECIFICATION OF SAFETY PARAMETERS. This is a minimal risk study. Patients enrolled in the RCT will receive a standard care behavioral intervention from their health care providers (brief counseling plus Quitline counseling) vs provider brief counseling plus the addition of 6 sessions of nurse delivered counseling vs brief physician counseling + multisession nurse delivered counseling +NRT. Eligibility for NRT will be assessed at the time study eligibility is assessed and prior to enrollment. It is important to note that the nicotine gum is an over-the-counter medication, proven safe, with minimal potential side effects. In addition, there are no significant interactions between NRT and HIV treatments (<http://www.hivdruginteractions>). Patients with a recent history of MI (four weeks), uncontrolled hypertension, arrhythmia, or worsening angina pectoris will not be eligible to enroll. Potential side effects related to NRT will be assessed by the nurse counselor at each counseling visit and reported in the tracking form that counselors use to document visits. The length of treatment with NRT (6 weeks) will generally coincide with those visits. At the time of enrollment participants in the nicotine gum arm will be told of the common side effects (e.g., Rash, mouth, tooth, or jaw problems, palpitations) they may experience and asked to report any problems to the nurse and/or doctor in the clinic or to call the contact number on the consent form. They will also be told how to reduce the likelihood of common side effects, including not smoking while using the gum. Counselor training will include information about potential side effects and to explore potential reasons for side effects and suggest ways to reduce side effects. The PIs will be contacted within 24 hours if the physician or counselor believes there is an AE or SAE, otherwise, forms will also be reviewed by the ISMS and NYU PIs weekly to assess the need to reduce the dose or discontinue the medication.

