8.3 TIME PERIOD AND FREQUENCY FOR EVENT ASSESSMENT

The occurrence of an AE or SAE may come to the attention of study personnel during a clinic visit with the provider or the nurse counselor during the intervention period or telephone surveys at 3 months). All AEs, including local and systemic reactions not meeting the criteria for SAEs, will be captured on the appropriate reporting form. Information to be collected includes event description, time of onset, participants' self-assessment of severity, relationship to study product, and time of

resolution/stabilization of the event. All AEs occurring while in the study will be documented appropriately regardless of relationship. All AEs will be followed to adequate resolution.

Any medical condition that is present at the time that the participant is screened will be considered as baseline and not reported as an AE. However, if the study participant's condition deteriorates at any time during the study, it will be recorded as an AE. UPs will be recorded in the data collection system throughout the study.

Changes in the severity of an AE will be documented to allow an assessment of the duration of the event at each level of severity to be performed. AEs characterized as intermittent require documentation of onset and duration of each episode.

The PI will record all reportable events with start dates occurring any time after informed consent is obtained until 7 (for non-serious AEs) or 30 days (for SAEs) after the last day of study participation. At each study visit, the investigator will inquire about the occurrence of AE/SAEs since the last visit. Events will be followed for outcome information until resolution or stabilization. All unresolved adverse events will be followed by the investigator until the events are resolved, the subject is lost to follow-up, or the adverse event is otherwise explained. At the last scheduled visit, the investigator will instruct each subject to report any subsequent event(s) that the subject, or the subject's personal physician, believes might reasonably be related to participation in this study. The investigator will notify the study sponsor of any death or adverse event occurring at any time after a subject has discontinued or terminated study participation that may reasonably be related to this study.

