8.6. REPORTING PROCEDURES – NOTIFYING THE FDA (NA)

8.7. HALTING RULES. (NA) This is a minimal risk study. Only those participants randomized to receive the over the counter drug, nicotine gum, will be receiving medication. If patients who are receiving NRT experience side effects these will be addressed as described above. If they must discontinue the nicotine gum they can still choose to continue to participate in the counseling component of the intervention.

8.8. SAFETY OVERSIGHT. It will be the responsibility of the PIs to oversee the safety of the study. This safety monitoring will include careful assessment and appropriate reporting of AEs and SAEs as noted above, as well as the construction and implementation of a site data and safety-monitoring plan. Safety oversight will be under the direction of a DSMB composed of individuals with the appropriate expertise, including a tobacco use treatment expert, an HIV expert and a biostatistician. The DSMB will meet at least semiannually to assess safety and efficacy data on each arm of the study. The DSMB will operate under the rules of an approved charter that will be written and reviewed at the organizational meeting of the DSMB. Each data element that the DSMB needs to assess will be clearly defined. The DSMB will provide its input to Drs. [name] and [name]. The primary responsibilities of the DSMB are to 1) periodically review and evaluate the accumulated study data for participant safety, study conduct and progress, and, when appropriate, efficacy, and 2) make recommendations concerning the continuation, modification, or termination of the trial. The DSMB will consider study-specific data as well as relevant background knowledge about the intervention, or patient population under study.

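### Side effects are sought more often in Arms 2 and 3 than in Arm 1, and the plan does not secure identical questioning in Arm 2, the gum's natural safety comparator

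*Combined protocol and SAP*

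**What the plan says.** Section 8.1 gives the only repeated symptom enquiry that the plan describes: "Potential side effects related to NRT will be assessed by the nurse counselor at each counseling visit". Under 6.3.2 those visits belong to two arms. The team will "provide a packet for each patient randomized to ARM 2 or 3 to the designated nursing staff", and "Patients will receive 4 sessions in the first 4 weeks and sessions at 8 and 12 weeks". For Arm 1, beyond the provider's brief intervention, the same section provides a call from an outside service: "The research team will send patient contact information to the Quitline which will proactively call the patient". The Quitline is given no part in collecting adverse events (AEs).

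Gum is confined to one arm (section 4.1): "Only ARM 3 participants will receive NRT". It starts after the first session (6.3.2): "At the end of the first session patients will be taken to the pharmacists".

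Section 8.3 says AEs may come to light at "a clinic visit with the provider or the nurse counselor during the intervention period or telephone surveys at 3 months". It also requires the investigator to ask about AEs at every study visit, and all AEs to be documented whatever their cause. Section 7.1.3 lists the patient visits as the baseline, 3-month and 6-month surveys, with a carbon monoxide test for those who report abstinence at 6 months.

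On review, 8.8 states: "The DSMB will meet at least semiannually to assess safety and efficacy data on each arm of the study". Section 9.3 limits the interim work to descriptive statistics.

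**The concern.** Mild, transient symptoms are recorded mainly when somebody asks. The events named in 6.1.5 and 8.1 (palpitations, nausea, light-headedness, rash, mouth problems) also occur without gum. An Arm 3 count therefore means little without a comparator collected in the same way.

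Two comparisons are affected, for different reasons. Against Arm 1, the frequency of asking differs by design. Against Arm 2, the frequency is the same but the content may not be. The enquiry is framed around a drug that Arm 2 does not receive, the nurse manual adds NRT material for Arm 3 only, only gum patients are told at enrollment what to look out for, and the trial is unblinded.

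The DSMB advises on continuing, modifying or stopping the trial, and nothing in the plan tells it that enquiry differs by arm. It could take more frequent asking for a gum effect, or dismiss a real gum effect as more frequent asking.

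**Working it through.** The plan gives no safety event rate, safety sample size or safety test, so there is no stated figure to reproduce. What can be checked is the number of planned enquiries per patient.

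**Inputs.** Counseling sessions fall in weeks 1, 2, 3, 4, 8 and 12 (6.3.2, Table 2). Surveys common to all arms fall at 3 and 6 months (7.1.3). Section 8.3 names only the 3-month survey as a source of AEs, but its rule of asking at each study visit would add the 6-month one. Both counts are shown. Provider visits are open to all arms but unscheduled for this purpose, and are left out.

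| | Arm 1 | Arm 2 | Arm 3 |
|---|---|---|---|
| Counseling sessions | 0 | 6 | 6 |
| Surveys | 1 to 2 | 1 to 2 | 1 to 2 |
| Total | 1 to 2 | 7 to 8 | 7 to 8 |

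Arm 3 minus Arm 1 = 6. Arm 3 minus Arm 2 = 0, provided that Arm 2 patients are actually asked.

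**During gum use.** Gum lasts 6 weeks from the end of session 1. Sessions in weeks 1 to 4 fall in that period, but session 1 precedes the first supply. That leaves three sessions (weeks 2, 3 and 4) against none scheduled in Arm 1. Weeks 8 and 12 come afterwards and can capture gum-period symptoms only by recall.

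**Two readings of 8.1.**

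- If every counseled patient is asked, Arms 2 and 3 are both raised relative to Arm 1, and Arm 3 v Arm 2 is fair on schedule.
- If counselors ask only gum patients, because the enquiry concerns NRT, Arm 3 is raised relative to both other arms. The rule in 8.3 does not settle this, because 7.1.3 does not list counseling sessions among the patient study visits.

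**Illustration of size (assumed values, none from the documents).** Let the true risk of a symptom be 20% in both arms, with detection of 90% in a counseled arm and 30 to 70% in Arm 1.

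- Recorded risk, counseled arm: 0.20 × 0.90 = 18%.
- Recorded risk, Arm 1: 0.20 × 0.30 = 6% to 0.20 × 0.70 = 14%.
- Apparent risk ratio: 0.90/0.70 = 1.3 to 0.90/0.30 = 3.0.
- With 208 per arm (13 sites × 16): 208 × 0.18 = 37 patients against 208 × 0.06 = 12 to 208 × 0.14 = 29.
- With 224 per arm (672/3): 224 × 0.18 = 40 patients against 224 × 0.06 = 13 to 224 × 0.14 = 31.

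The ratio depends only on the two detection rates. The enquiry counts explain why those rates should differ, but do not determine by how much.

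**The case against.** A reader might infer that the gum arm has no clean comparator at all. The documents do not support that. Arms 2 and 3 share the same trained nurses and the same six sessions, and the main planned difference between them is the gum. On schedule, Arm 2 is a good comparator, and 8.1 does not expressly limit the enquiry to Arm 3. What remains is that the plan does not say the same questions are asked in both arms, and the wording gives a counselor reason to skip them in Arm 2.

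A reader might also infer that AEs in Arm 1 go unsought. That is not so either. The general rules in 8.3 apply to every arm, provider visits are a listed route, and enquiry at both surveys is implied. This reduces the gap but does not close it: a survey at 3 months is a weak substitute for questions asked within a week or two.

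The strongest objection concerns consequence. Unequal contact is inherent in a pragmatic trial of counseling intensity. Safety is not an endpoint (4.2), interim work is descriptive (9.3), halting rules are marked not applicable (8.7), and the counselor enquiry mainly serves individual care. Deaths and hospital admissions depend far less on how often patients are asked. The DSMB includes a biostatistician and will have a charter that defines its data elements. All of this stands and limits the severity. It does not remove the problem: a board judging from descriptive tables, without a formal rule, especially needs to know how the counts arose.

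**Conclusion.** The concern holds in two parts. First, as written, by-arm safety data are open to ascertainment bias in any comparison with Arm 1: 1 to 2 scheduled enquiries there against 7 to 8 with counseling, and none against three during gum use after the first supply. The direction is clear if asking more often finds more symptoms. Second, Arm 3 v Arm 2 is matched on contact but not assuredly on questioning.

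The size is not known. The apparent ratio of 1.3 to 3.0 illustrates assumed detection rates. It should not be read as a forecast, nor as the result of a significance test, since none is planned for safety. It concerns mild, transient symptoms rather than serious events. Severity is minor to moderate. The change is worth making because it is cheap and protects the only safety comparison that isolates the gum.

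**What to change.** 1. In 8.1, state that counselors put the same symptom questions to Arm 2 and Arm 3 patients at the same sessions, worded without reference to NRT. Name Arm 3 v Arm 2 as the gum safety comparison.
2. For any comparison with Arm 1, use only events elicited by one identical AE question in the 3- and 6-month surveys of all arms. Reconcile 8.3 accordingly: its list of sources stops at the 3-month survey, while its general rule covers every study visit.
3. Give the DSMB counselor-collected and survey-collected events in separate tables, with a note on how often each arm is asked.
4. Reconcile 8.3, which documents all AEs, with 8.4.1, which can be read as leaving expectable, non-harmful events unrecorded. This decides which symptoms reach the tables.

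The cost is a few minutes per Arm 2 session on an existing form, one common survey item and a split table. The downside is that more minor, unrelated symptoms will be recorded in Arm 2.

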8.1.1. Definition of Adverse Events

An adverse event (AE) is any symptom, sign, illness or experience that develops or worsens in severity during the course of the study. Intercurrent illnesses or injuries should be regarded as adverse events. Abnormal results of diagnostic procedures are considered to be adverse events if the abnormality:

- results in study withdrawal
- is associated with a serious adverse event
- is associated with clinical signs or symptoms
- leads to additional treatment or to further diagnostic tests
- is considered by the investigator to be of clinical significance

8.1.2 Definition of Serious Adverse Event

Adverse events are classified as serious or non-serious. A serious adverse event is any AE that is:

- fatal
- life-threatening

- requires or prolongs hospital stay
- results in persistent or significant disability or incapacity
- a congenital anomaly or birth defect
- an important medical event

Important medical events are those that may not be immediately life threatening, but are clearly of major clinical significance. They may jeopardize the subject, and may require intervention to prevent one of the other serious outcomes noted above. For example, drug overdose or abuse, a seizure that did not result in in-patient hospitalization, or intensive treatment of bronchospasm in an emergency department would typically be considered serious. All adverse events that do not meet any of the criteria for serious are regarded as non-serious adverse events.

8.1.3. Definition of Unanticipated Problems

Any incident, experience, or outcome that meets all of the following criteria:

- Unexpected in nature, severity, or frequency (i.e. not described in study-related documents such as the IRB-approved protocol or consent form, the investigators brochure, etc)
- Related or possibly related to participation in the research (i.e. possibly related means there is a reasonable possibility that the incident experience, or outcome may have been caused by the procedures involved in the research)
- Suggests that the research places subjects or others at greater risk of harm (including physical, psychological, economic, or social harm).

8.2. CLASSIFICATION OF AN ADVERSE EVENT

8.2.1. Severity of Event

For AEs not included in the protocol defined grading system, the following guidelines will be used to describe severity.

- **Mild** – Events require minimal or no treatment and do not interfere with the participant's daily activities.
- **Moderate** – Events result in a low level of inconvenience or concern with the therapeutic measures. Moderate events may cause some interference with functioning.
- **Severe** – Events interrupt a participant's usual daily activity and may require systemic drug therapy or other treatment. Severe events are usually potentially life-threatening or incapacitating.

8.2.2. Relationship to the study agent. The PIs will assess if the AE is related or not related to the NRT.

- **Related** – The AE is known to occur with the study agent, there is a reasonable possibility that the study agent caused the AE, or there is a temporal relationship between the study agent and event. Reasonable possibility means that there is evidence to suggest a causal relationship between the study agent and the AE.
- **Not Related** – There is not a reasonable possibility that the administration of the study agent caused the event, there is no temporal relationship between the study agent and event onset, or an alternate etiology has been established.

8.2.3. Expectedness. [name] and [name] will be responsible for determining whether an AE is expected or unexpected. An AE will be considered unexpected if the nature, severity, or frequency of the event is not consistent with the risk information previously described for the study agent.

